### 7.3 Steps to Minimize Risks

Fetal risks:

The fetal procedures will be performed by specialists in fetal medicine with extensive experience in fetoscopy as well as FETO.

This is not an open study and eventual extension of the study consortium will be made dependent on a decision of the steering committee.

Maternal risks:

- Maternal infectious complications: prophylactic administration of intravenous antibiotics.
- Complications and side effects of epidural analgesia (if applied): the procedure will be carried out or under the direct supervision of an expert in this procedure.
- Preterm labor induced by the intervention: prophylactic administration of tocolytics.
- Maternal uterine / placental bleeding: ultrasound guidance of trocar insertion.

The FETO procedure and neonatal management of the patients will be undertaken in major university hospitals with multidisciplinary teams of experts familiar with both pre- and postnatal management of CDH and FETO.

## 7.4 Risk Balance Summary

Severe CDH (O/E LHR of less than 25%) is associated with high rates of mortality (more than 70%) and morbidity. In such cases FETO has been introduced as an alternative to the options of termination of pregnancy and expectant management. There is evidence from experience of more than 150 cases treated by FETO that the survival rate is improved. There is also evidence that this increased survival is not at the expense of an increased short term morbidity. In contrast survivors seem to have less morbidity than can be expected based on severity (O/E LHR).

The rationale for the proposed study is that in cases of moderate CDH, FETO in the third trimester would reduce morbidity and may increase survival.

On the basis of our current experience with FETO there is no apparent serious risk for the mother. The main risk for the fetus is iatrogenic prematurity which in this study is minimized by performing the procedure in the third trimester.

A randomized clinical trial is the only way to answer this question. If the results are favorable, we will offer a new therapeutic modality to future patients. If not favorable, we will have prevented untimely spread of this new operation that would have claimed benefits without scientific basis.

By

## 8.0 BENEFITS

The hypothesis is that prenatal intervention will improve morbidity, lung development and growth or survival in patients with isolated, moderate CDH. We do not know at this stage of the trial whether in fetuses with moderate diaphragmatic hernia FETO is beneficial or not. The results of this study will help us to manage moderate diaphragmatic hernia better in the future.

Although the FETO procedure has shown promise as an intervention for severe and extremely severe CDH, moderate CDH has not been studied adequately in the United States. This study will help extend current trials of FETO to include the population of the United States.

Even though the FETO procedure creates risks, the chance of the baby's survival is still probably much better with a successful FETO procedure. We believe the benefits will outweigh the risks. Risk to benefit ratio is favorable.

## 9.0 STATISTICAL CONSIDERATIONS

### 9.1 Sample Size and Precision

Primary endpoint has been changed to survival at discharge. Initially, it was estimated that 55% of patients in control arm would be alive at discharge. Given that we have decided that an absolute increase in survival rate of 20% in FETO arm would be an improvement, clearly clinically relevant and realistic, we'd then assume a survival rate of 75% in FETO arm to determine sample size. An absolute increase of 15% would still be acceptable. Although it is of importance in this trial to

avoid continuation when there is evidence of effectiveness of FETO, it'd be undesired to underestimate the required sample size because of an overestimated survival rate in control arm. Therefore, we decided to use data from administrative review to estimate sample size. This resembles the internal pilot study method by Friede and Kieser. Using the overall average survival rate over the two groups (blinded data), which was 50.1%, we'd therefore use 40% vs 60% survival rate in control vs FETO arm. Based on blinded procedure, the size of the 'internal pilot', and the fact that an overall response rate of 50% maximizes required sample size there is no need to adjust type I and II error rates.

We use a group sequential design with overall one-sided alpha of 2.5% and a power of 80%. Formal interim analyses are scheduled for efficacy only, although the DMC retains the right to stop the trial for clear futility. We adopted the O'Brien-Fleming method to derive critical boundaries to stop the trial for efficacy. Five interim analyses are planned, after 40, 60, 70, 80, and 90% of sample size at final analysis. Using the abovementioned parameters and z-test for the difference in proportions, critical boundaries are obtained using PROC SEQDESIGN in SAS v9.3 (SAS Institute, Cary, USA).

Analysis	N per arm	Efficacy boundary	
		Difference in survival rates	p-value
Interim 1	40	0.365	0.0005
Interim 2	59	0.243	0.0036
Interim 3	69	0.209	0.0064
Interim 4	79	0.182	0.0099
Interim 5	89	0.162	0.0140
Final	98	0.146	0.0186

When deriving a sample size plan including formal boundaries to stop for futility, the overall sample size hardly changed. As a result, we left stopping for futility at the discretion of the Data Safety Monitoring Committee (DSMC).

## 9.2 Proposed Analysis

Achieved significance rule:

The initially anticipated increase in survival at discharge was 20%, yet at the moment of design of the trial no data on outcomes on percutaneous FETO with a balloon for moderate hypoplasia were known.

There is no stratification prior to or post randomization.

**Null Hypothesis:** The null hypothesis to be tested is that there is no difference in survival and in number of survivors requiring supplemental oxygen at the age of 6 months between fetuses managed expectantly during pregnancy versus those undergoing antenatal therapy.

Stopping rule:

The trial will be discontinued if there is a significant difference for the primary outcome measure (survival at discharge) at the foreseen time points of analysis. The DSMC, however, may consider continuation of the study in an adapted design to determine whether significance can be achieved for the co-primary variable (oxygen need at 6 months of life).

The DSMC is a group of physician and ethicist experts from Baylor College of Medicine who are

not otherwise involved with the study. The DSMC will assess, on an ongoing basis, the study conduct and monitor the safety of current and future patients as well as the validity and scientific integrity of the trial. The DSMC will meet to review data and will recommend continuation, modifications to the study design or discontinuation of the study. The DSMC will advise the Principal Investigator (PI) and study staff of any issues after the meetings.

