## 2.1 Report of Prior Investigations

Fetuses with CDH presenting with liver herniation and a lung area-to-head circumference ratio (LHR) of less than 1.0 have a high chance for neonatal death due to pulmonary hypoplasia. Fetal tracheal occlusion (TO) prevent egress of lung liquid, and this has been shown to trigger lung growth. Initially animal experiments showed that a minimally invasive technique for Fetoscopic Endoluminal Tracheal Occlusion (FETO) with a detachable balloon was possible and effective in reducing lung hypoplasia from CDH.

In 2001, Deprest et al demonstrated the feasibility of FETO by percutaneous access, using a fetoscope, in fetuses with severe CDH. In a retrospective multicenter review, the same group obtained LHR measurements and noted the position of the liver in 134 babies with isolated left-sided CDH between 26 and 28 weeks gestation. The overall survival of the live born babies was 47% (58/123). The LHR and position of the liver both had a direct correlation with subsequent survival. A combination of both variables best predicted neonatal outcome: the presence of the liver in the chest and a LHR < 1.0 predicted a survival of 9%. When the LHR was < 0.6, there were no survivors irrespective of liver position. Deprest's group successfully performed endotracheal placement of the FETO balloon in 20 cases at a median gestational age of 26 weeks. The mean duration of the operation was 22 (range 5-54) minutes. In 11 (55%) of these patients, there was postoperative preterm (i.e., <37 weeks) rupture of the membranes (PPROM). The membranes ruptured before 32 weeks in 35% of cases, with a decreasing trend as experience increased. Ultrasound scans after FETO demonstrated an increase in the echogenicity of the lungs within 48 hours and improvement in the LHR from a median 0.7 (range 0.4-0.9) before FETO to 1.8 (range 1.1- 2.9) within 2 weeks after surgery. The median gestation at delivery was 33.2 (range 27-38) weeks, and in 14 (70%) this occurred after 32 weeks.

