#### Methods of analysis

We will analyze the primary and co-primary endpoints with the z-test for unpaired proportions (equal to the Pearson chi-square test) using a one-sided alpha of 2.5%. To control for multiplicity, we will use a hierarchical approach. If the trial is stopped for efficacy for the primary endpoint (survival at discharge) at one of the interim analyses based on the z-test, we will evaluate the co-primary endpoint (survival without oxygen dependency at 6 months) with the same test. As explained in the sample size section, the DSMC first decides whether more patients in the FETO arm have to be recruited in order to reach the required sample size. If it is not feasible to reach the required sample size, we will not perform the z-test for the co-primary endpoint.

For the primary and co-primary endpoints, we will compute the difference in proportions between the study arms as well as the relative risk, both with a standard two-sided 95% CI. These results are at least as important as the determination of statistical significance based on the z-test.

For the secondary endpoints, we will not perform statistical testing. For categorical endpoints, we will compute relative risks and differences in proportion with their respective 95% confidence intervals. For continuous endpoints, we will compute 95% confidence intervals on the difference in medians using the percentile bootstrap method. We will analyze time-to-event outcomes (days to discharge from neonatal intensive care unit, days until end of ventilatory support, days until release from ECMO support, days until full enteral feeding) with a 95% confidence interval for the median cumulative incidence of the event, with death used as a competing event 

Sources of error:

- The power of the study will be adversely affected by patient's non-compliance with the randomly assigned regimen.

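### The primary effect estimate is unadjusted although O/E LHR, which the protocol calls prognostic, is measured in every fetus at entry; the test is valid, but precision is lost and chance imbalance is left uncorrected

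*Combined protocol and SAP*

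**What the plan says.** On design, Section 9.2 says "There is no stratification prior to or post randomization".

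On analysis, Section 9.2 (Methods of analysis) says "We will analyze the primary and co-primary endpoints with the z-test for unpaired proportions (equal to the Pearson chi-square test"), one-sided at 2.5%. For the effect size, "we will compute the difference in proportions between the study arms as well as the relative risk", each with a 95% CI. The same paragraph ranks these estimates as no less important than the significance test.

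On prognosis, Section 2.1 reports "The LHR and position of the liver both had a direct correlation with subsequent survival" and adds that the two together predicted best. Section 2.0 says that LHR before the procedure also predicts outcome after FETO.

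On availability, Section 5.2 makes O/E LHR at study entry part of eligibility. Section 6.1 schedules ultrasound and MRI before intervention in both groups. In the analysis section, liver position appears only as a secondary prenatal outcome.

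No section plans an analysis adjusted for or stratified by either variable, even as a sensitivity analysis. The only grouping factor named is postnatal centre case load.

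**The concern.** A baseline value that predicts the outcome can be used to narrow the confidence interval and to correct the estimate for an uneven split between arms. Here it is collected anyway and then left out of both the test and the estimate. If more of the worse-prognosis fetuses fall into one arm by chance, the crude difference carries that imbalance, and the plan has no pre-specified way to show how much of the result it explains.

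The plan already recognises the general problem. Section 9.2 notes that undiagnosed anomalies may fall unevenly between the arms, and answers by excluding those cases. The principal known predictors get no handling, although adjustment would need no exclusions. An adjustment chosen after an imbalance has been seen would carry little weight.

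**Working it through.** **1. The plan's own figure.** Section 9.1: "we'd therefore use 40% vs 60% survival rate in control vs FETO arm"; "We use a group sequential design with overall one-sided alpha of 2.5% and a power of 80" per cent; "Five interim analyses are planned, after 40, 60, 70, 80, and 90% of sample size at final analysis"; O'Brien-Fleming bounds used "to derive critical boundaries to stop the trial for efficacy".

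- Bounds c/√t at t = 0.4, 0.6, 0.7, 0.8, 0.9, 1, solved for one-sided 2.5%: c = 2.083. The nominal p-values are 0.0005, 0.0036, 0.0064, 0.0099, 0.0140 and 0.0186, as in the table.
- Drift for 80% power is 2.855. Variance term: 0.4×0.6 + 0.6×0.4 = 0.48. n = 2.855² × 0.48 / 0.20² = 97.8, so 98 per arm. Power at 98 is 80.1%.
- Final difference boundary: 2.083 × √(0.48/97.8) = 0.146, as in the table.

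The sample size and boundaries are therefore correct for the unadjusted test.

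**2. Gain from adjustment.** The documents give one pooled survival figure for the moderate band (60% or lower), so the gap between better- and worse-prognosis fetuses has to be assumed. Take a two-level factor with half the fetuses in each level.

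- Share of outcome variance explained: R² = 0.25 × gap² / 0.24.
- Residual variance is multiplied by (1 − R²), so n = 97.8 × (1 − R²). The boundaries are unchanged.
- 95% CI half-width at 98 per arm: 1.96 × √(0.48 × (1 − R²)/98).

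| Assumed gap | R² | Power at 98 per arm | n per arm for 80% power | Fewer per arm | CI half-width |
|---|---|---|---|---|---|
| none | 0 | 80.1% | 97.8 | – | 13.7 points |
| 10 points | 0.010 | 80.5% | 96.8 | 1 | 13.6 |
| 20 points | 0.042 | 81.7% | 93.7 | 4 | 13.4 |
| 30 points | 0.094 | 83.8% | 88.6 | 9 | 13.1 |

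A simulation (200,000 trials per case, one look at one-sided 2.5%, 98 per arm) compared the crude z-test with a stratified Cochran-Mantel-Haenszel test. Crude power was 81.5%, 81.2% and 81.4% at gaps of 10, 20 and 30 points; stratified power was 80.9%, 81.8% and 84.1%. At 10 points there is no visible gain, partly because the crude test runs slightly above its nominal level. Simulated type I error was about 2.7% crude and 2.4–2.5% stratified.

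**3. Chance imbalance.** For a 50:50 factor, the SD of the between-arm difference in its prevalence is √(2 × 0.25/n).

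- n = 98: SD = 0.0714. P(imbalance of 10 points or more, either direction) = 2 × [1 − Φ(0.10/0.0714)] = 2 × [1 − Φ(1.40)] ≈ 16%.
- n = 69 (third look): SD = 0.0851. 2 × [1 − Φ(1.17)] ≈ 24%.
- Shift in the crude difference = imbalance × gap: 0.10 × 0.10, 0.20 or 0.30 = 1, 2 or 3 points. The boundary is 20.9 points at 69 per arm and 14.6 at 98.

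**The case against.** The strongest reply is that nothing in the plan is wrong. An unadjusted test is a legitimate choice, its standard error already allows for chance imbalance over repeated randomisations, and the power calculation reproduces. All of that stands.

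A reader might go further and infer that the crude analysis is biased or inflates the false-positive rate. The documents and the check do not support that. Given a 14-point imbalance favouring FETO and a 20-point gap, the conditional one-sided error at a single 2.5% look with 98 per arm would be about 5.5%, but the opposite imbalance gives about 0.8%, and the average stays near nominal. Only half of the imbalances counted above favour FETO.

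Four further limits also stand:

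- **The gap is assumed.** The predictive evidence in Section 2.1 concerns raw LHR over a wider severity range than this trial enrols. Its extreme figures cannot be carried into the 25–44.9% O/E LHR band.
- **Eligibility is not a full cross of the two factors.** Fetuses at 35–44.9% qualify only with liver herniation, so liver-down fetuses occur only at 25–34.9%. The favourable level of one factor is tied to the unfavourable level of the other, which may narrow the gap.
- **Liver position at entry is not shown for everyone.** It can be inferred from the baseline imaging, but the lower band is eligible whatever the liver position.
- **The smallest look appears to be past.** Section 9.2 refers to data already inspected at two interim analyses, so an argument from imbalance at 40 per arm has no practical bearing now. The O'Brien-Fleming bound was also strictest there.

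These points limit the size of the concern. They do not explain why a prognostic baseline value required for eligibility has no role in the effect estimate.

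**Conclusion.** The point holds as a modest, inexpensive improvement. The plan gives up precision and leaves chance imbalance uncorrected in an estimate that it ranks level with the test. The test is valid and the sample size is right.

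The size of the loss is uncertain. Under an assumed 50:50 factor and gaps of 10 to 30 points, adjustment is worth about 0.4 to 3.7 points of power, or 1 to 9 patients per arm. An imbalance of 10 points would move the crude difference by 1 to 3 points. At the low end the precision gain is negligible, and the remaining benefit is a pre-specified answer to any imbalance that occurs. These figures concern survival to discharge only.

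**What to change.** - **Leave the stopping rule alone.** Keep the crude z-test and the existing boundaries for all remaining looks. They were derived for that statistic, and changing it mid-trial would need its own check of error control.
- **Pre-specify the adjusted estimate before the next unblinded look.** Report a standardised (marginal) risk difference and relative risk with 95% CIs, for example from logistic regression, adjusted for baseline O/E LHR as a continuous variable. Make this the main effect estimate and show the crude one beside it.
- **Add liver position once its baseline capture in all fetuses is confirmed.**
- **If Mantel-Haenszel is preferred, use the three strata that exist:** O/E LHR 25–34.9% liver up, 25–34.9% liver down, and 35–44.9% liver up. The fourth combination is ineligible.

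Cost: a protocol/SAP amendment, which under Section 10.1 needs prior IRB and FDA approval, and minor analysis work. O/E LHR needs no new data collection. The adjusted estimate may differ slightly from what the crude stopping test implies, so the plan should say in advance that the crude test governs stopping and the adjusted estimate describes the size of the effect.

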#### Primary Analysis:

The primary analysis will compare the proportion of subjects who are surviving till discharge and the survivors requiring no oxygen at 6 months of age. The primary analysis will be based on the intent-to-treat principle.

#### Secondary Analyses:

A secondary analysis will compare the proportion of subjects that survived until discharge from the hospital in the two treatment groups, and those free of oxygen need at 6 months of age with an as-treated (“per protocol”) analysis.

Data will also be analyzed depending on the case load at each postnatal treatment center, i.e. treatment centers with a case load above, respectively under 6/year.

Whenever possible, analysis of outcomes of non-randomized subjects will be made to provide the most complete synthesis of the data. We will keep data from any non-randomized patient that receives a FETO balloon on a compassionate basis and we will analyze the data in a separate analysis.

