## 5.2 Inclusion Criteria

FETUSES:

1. Left-sided diaphragmatic hernia
2. Fetuses presenting at the latest at 31 weeks plus 5 days (intervention at the latest on 31 weeks plus 6 days).
3. Severity: Predicted moderate pulmonary hypoplasia. The degree of hypoplasia will be determined by the ultrasonographic measurement of the observed to expected lung area to head circumference ratio (O/E LHR) in a FETO center at entry to the study, at the latest the day before occlusion, but ideally between 26 and 31 weeks for practical reasons. (The O/E LHR is a measure that is gestational age independent.)

The following criteria for moderate pulmonary hypoplasia will be used: • O/E LHR 25-34.9% (included) irrespective of the liver position, or • O/E LHR 35-44.9% (included) with intrathoracic herniation of the liver.

In this group there is a predicted risk for postnatal death of 40% or higher and the risk of broncho-pulmonary dysplasia in case of survival is 33% or higher.

4. Chromosomally normal fetus.

5. Fetus with no major anomalies that would impact the clinical course or outcomes.

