- Preterm pre-labor rupture of the membranes and as a consequence preterm labor prior to in utero reversal of the occlusion, with as a consequence "incomplete" prenatal therapy as well as problems directly due to the inability or difficulties to remove the balloon, may result in lower than expected survival chances. When this happens, it will cause delivery at one of the FETO centers, therefore leading to a higher than expected number of babies delivered at these institutions. However this is inherent to the prenatal therapy and not avoidable. A separate secondary analysis may be done as to judge on the biological effect of the complete course of prenatal therapy (balloon insertion and balloon removal followed by birth in the un-occluded state), but again, results will be reported on an intention to treat - basis.
- In the fetal treatment arm there is the potential of patients not complying during the period the airways are plugged, presenting in an emergency at their local center, or for whatever reason not returning to the FETO center for balloon removal. This may adversely affect the outcome in the treatment group, lead to a higher than expected death rate in that arm. It could only be

discounted by post hoc exclusion. This will however not be done, as it is considered as an inherent risk of prenatal therapy. Such an effect may however be documented in a secondary analysis as described above.

- Prenatal medical imaging techniques may fail to recognize a concomitant congenital anomaly that is therefore only diagnosed after birth. Since serious associated anomalies are an independent predictor of outcome, and their numbers should be low, patients may not be equally distributed in both treatment arms. These patients will be excluded post hoc from analysis. It will include patients with serious genetic anomalies (not known at the time of FETO), undiagnosed structural cardiac or other structural anomalies that directly compromise neonatal outcome. Analysis of cases to be excluded will be overseen by the Data Monitoring and Safety Committee (also referred to as Oversight Committee).

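### The as-treated/per-protocol and complete-course secondary analyses sort pregnancies on events after randomisation: the complete-course one leans towards FETO, and the as-treated one in an uncertain direction

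*Combined protocol and SAP*

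**What the plan says.** Section 9.2 sets the main comparison by allocation: "The primary analysis will be based on the intent-to-treat principle". Under Secondary Analyses it then plans to compare survival to discharge and freedom from oxygen "at 6 months of age with an as-treated (“per protocol”) analysis". The two terms are run together. The plan does not say who would be moved between groups, who would be dropped, or how a pregnancy without a balloon is to be classed.

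The list of error sources in the same section discusses membrane rupture and preterm labour before the balloon is out. It says that these "may result in lower than expected survival chances", and adds: "A separate secondary analysis may be done as to judge on the biological effect of the complete course of prenatal therapy". The complete course is defined as "balloon insertion and balloon removal followed by birth in the un-occluded state". No comparison group is named. The sentence ends by saying that "results will be reported on an intention to treat - basis". The next item says that FETO-arm patients who do not return for balloon removal may raise the death rate in that arm. It rules out excluding them post hoc, but allows the effect to be shown in a secondary analysis.

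The same list foresees that control patients may obtain fetal intervention elsewhere. It gives no rate and mentions only a loss of power.

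**The concern.** An as-treated analysis moves each pregnancy to the group of the treatment it received. A per-protocol analysis drops those who did not adhere. They answer different questions and can be biased in different directions, so with neither defined the set could be chosen after the data are seen. Either way, membership depends on what happened after randomisation, and the groups are no longer those that randomisation made comparable.

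The complete-course analysis has the same defect in a sharper form. Having a balloon inserted, having it removed and being born with an open airway are conditions that only a FETO-arm pregnancy can fail. A control pregnancy with the same early delivery stays in its group unless the comparator is restricted.

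Timing leaves room for this before placement too. Severity is measured at entry, "at the latest the day before occlusion, but ideally between 26 and 31 weeks for practical reasons" (Section 5.2), and the balloon is placed at 30 weeks 0 days to 31 weeks 6 days (Section 4.0). A FETO-arm fetus lost or delivered in between would leave the treated group, while the same event among controls would count against control.

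At stake is a secondary estimate of benefit that could exceed the intention-to-treat result for reasons unrelated to the treatment.

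**Working it through.** **The plan's own figures.** The documents give no figure for either secondary analysis. The nearest is the design in Section 9.1: 40% v 60% survival, one-sided alpha 2.5%, 80% power, 98 per arm. It reproduces. A single-look test needs 97 per arm. Simulating the six looks with the stated p-value boundaries gives alpha 0.0249 and power 0.800 at 98 per arm. The 96 per group for 35% v 55% also reproduces. The 40% rate and 98 per arm are used below.

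**Complete course, no true effect (40% in both arms).** Let f be the share of the FETO arm with an incomplete course and s the survival in that share. Survival among completers is (0.40 − f·s)/(1 − f). Set against all controls, the spurious difference is that value minus 0.40, which equals f(0.40 − s)/(1 − f).

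The documents do not give f. As a proxy I use membrane rupture after FETO: 15% within 3 weeks (Section 2.0, severe CDH) and 11% to 35% (Section 7.2). The values of s, and the use of all controls as comparator, are assumptions.

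| f | s | Completers | Spurious difference |
|---|---|---|---|
| 11% | 20% | 0.378/0.89 = 42.5% | +2.5 points |
| 11% | 0% | 0.400/0.89 = 44.9% | +4.9 |
| 15% | 20% | 0.370/0.85 = 43.5% | +3.5 |
| 15% | 10% | 0.385/0.85 = 45.3% | +5.3 |
| 15% | 0% | 0.400/0.85 = 47.1% | +7.1 |
| 35% (extreme) | 10% | 0.365/0.65 = 56.2% | +16.2 |

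At f = 15% and s = 10%, with 98 randomised per arm, the chance that z exceeds 1.96 at a single unadjusted look is 10.7% instead of 2.5%. With a true 60% v 40%, the same f and s give (0.60 − 0.015)/0.85 = 68.8%, so a 20-point effect appears as 28.8.

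**Literal as-treated, no true effect.** Let x be the share of the FETO arm without a balloon, with survival s. Let y be the share of controls treated elsewhere, with survival r.

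- Treated group: (0.40 − x·s + y·r)/(1 − x + y)
- Untreated group: (0.40 + x·s − y·r)/(1 + x − y)

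The documents put failed positioning at 2% (Section 7.1) and failed tracheal access at under 4%, solved by a second attempt (Section 6.4.3). So x = 2% to 4%. The values of s, y and r are assumptions.

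| x | s | y | r | Treated v untreated | Difference |
|---|---|---|---|---|---|
| 2% | 0% | 0 | – | 40.8% v 39.2% | +1.6 points |
| 4% | 0% | 0 | – | 41.7% v 38.5% | +3.2 |
| 4% | 20% | 0 | – | 40.8% v 39.2% | +1.6 |
| 2–4% | 40% | 0 | – | 40.0% v 40.0% | 0 |
| 4% | 60% | 0 | – | 39.2% v 40.8% | −1.6 |
| 4% | 0% | 5% | 20% | 40.6% v 39.4% | +1.2 |
| 4% | 0% | 10% | 20% | 39.6% v 40.4% | −0.8 |
| 2% | 20% | 10% | 20% | 38.5% v 41.7% | −3.2 |

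With no true effect, the expected intention-to-treat difference is 0 in every one of these scenarios.

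**The case against.** A reader might infer that both analyses are bound to favour FETO. The documents do not support that for a literal as-treated analysis. Section 9.2 foresees controls who are treated elsewhere and states neither their number nor their prognosis, and the table shows that the sign can change. Cases whose placement failed may also survive at the average rate, and the bias is then zero. This objection stands.

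A reader might also want larger figures. Nothing in the documents supports a non-placement rate above 4%. That figure covers technical failure and not every route to having no balloon. Loss between entry and placement is possible, but neither the interval from randomisation to placement nor a loss rate is given, so it cannot be sized.

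Membrane rupture is an imperfect stand-in for an incomplete course. It comes from severe disease, and Section 6.6.2 provides for prolonging the pregnancy and for puncture or retrieval after rupture, so a ruptured case can still complete the course. For that reason 35% is an upper extreme. The plan also does not say that completers would be set against all controls; that is an assumption in the working.

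Lastly, the safeguards are real. Intention to treat is primary and is still reported, stopping depends on the primary outcome, and the complete-course analysis is optional. To infer that the trial's main conclusion is at risk would go beyond the documents. What the objection does not remove is that the plan commits to one undefined analysis and permits another that selects on outcomes of treatment, with no caveat on either.

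**Conclusion.** The point holds in a limited form. Both analyses group or select pregnancies on events after randomisation, and the first merges two different methods.

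- **Complete course, or a per-protocol set that drops FETO-arm non-adherers:** the bias favours FETO by the plan's own reasoning, since it expects the removed cases to survive less often. The size for the complete course is about +2.5 to +7 points, given 11–15% incomplete, 0–20% survival in those cases and all controls as comparator. If a per-protocol set also dropped controls treated elsewhere, their prognosis would matter too.
- **Literal as-treated:** the direction is uncertain. The bias is 0 to about +3.2 points at 2–4% failed placement with 0–40% survival and no crossover. It turns negative if enough poor-prognosis controls obtain FETO elsewhere, or if cases without a balloon do better than average.

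The sizes are for survival to discharge. The oxygen endpoint was not sized separately. The effect is confined to secondary results, so this is a desirable correction and not a threat to the primary analysis.

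**What to change.** Under Secondary Analyses in Section 9.2, replace the as-treated/per-protocol analysis with a complier average effect that uses randomisation as the instrument: the intention-to-treat difference divided by the between-arm difference in the proportion with a balloon placed, with a 95% CI. This also takes account of control crossover. State the assumption that allocation affects outcome only through placement, and note that a failed attempt may itself affect outcome, because it still involves entry into the uterus. At 2–4% non-placement without crossover the result stays close to intention to treat: a 20-point difference becomes 20/0.98 = 20.4 to 20/0.96 = 20.8.

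If the complete-course analysis is run, add to Section 9.2:

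- its comparator, namely controls still undelivered at the same gestation (a landmark comparison);
- the label exploratory and non-randomised;
- a statement that the expected bias favours FETO and that the landmark removes only part of the selection, since FETO is itself associated with earlier delivery (Section 2.0).

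The cost is SAP wording, one short extra analysis and a slightly wider interval. The primary analysis, the stopping rule, the sample size and the conduct of the trial do not change.
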